### 9.3 Gender and Minority Accrual Estimates

The gender and minority distribution of the study population is expected to be:

Accrual Targets			
Ethnic Category	Sex/Gender		
	Females	Males	Total
Hispanic or Latino	24	37	61
Not Hispanic or Latino	89	103	192
Ethnic Category: Total of all subjects	113	140	*253
Racial Category			
American Indian or Alaskan Native	3	0	3
Asian	2	10	12
Black or African American	8	8	16
Native Hawaiian or other Pacific Islander	0	0	0
White	100	122	222
Racial Category: Total of all subjects	113	140	*253

\* These totals must agree

This distribution was derived from P9645 and accounts for an aggregate ineligibility and inevaluability rate of 10%.

## 10.0 EVALUATION CRITERIA

### 10.1 Common Terminology Criteria for Adverse Events v4.0 (CTCAE)

The descriptions and grading scales found in the revised NCI Common Terminology Criteria for Adverse Events (CTCAE) version 4.0 will be utilized for AE reporting beginning July 1, 2011. All appropriate treatment areas should have access to a copy of the CTCAE version 4.0 and a copy can be downloaded from the CTEP website (<http://ctep.cancer.gov>).

### 10.2 PRETEXT GROUPING (See [Appendix I](#))

PRETEXT will be assessed at diagnosis and at the time of all subsequent abdominal scans performed. PRE-OPERATIVELY. The group assigned after the second cycle of chemotherapy and where applicable, after the 4th cycle of chemotherapy, will be referred to as POST-TEXT.

The number of affected liver sections determines the PRETEXT group as shown in [Appendix I](#). The assignment of PRETEXT will be established by the consensus of the treating oncologist, radiologist, and surgeon at the local institution. Pre-operative abdominal scans will also be submitted for central radiologic and surgical review to assess concordance of local and central PRETEXT grouping.

The patient's liver tumor will be assigned PRETEXT (and/or POST-TEXT) according to the guidelines below. These guidelines are shown graphically in [Appendix I](#).

PRETEXT/POST-TEXT Group	Number of Affected Liver Sections
1	Tumor involves only 1 liver section; 3 adjoining sections are free of tumor.
2	Tumor involves 2 adjoining liver sections; 2 adjoining sections are free of tumor.
3	Tumor involves 3 adjoining sections or 2 nonadjoining sections; 1 section or 2 nonadjoining sections are free of tumor.
4	Tumor involves all 4 liver sections; there is no section free of tumor.
Any PRETEXT/POST-TEXT Group can be annotated with the following:	
+V	Tumor ingrowth of vena cava or ALL THREE hepatic veins
+P	Tumor ingrowth of main portal vein bifurcation or both right and left portal veins
+C	Tumor ingrowth of caudate lobe
+E	Extrahepatic contiguous tumor ingrowth of diaphragm, abdominal wall, bowel
+M	Distant metastatic disease

### 10.3 Response Criteria for Patients with Solid Tumors

This study will evaluate response using the Response Evaluation Criteria in Solid Tumor (RECIST) from the NCI for the evaluation of radiographic response. Response will also be evaluated using the tumor marker alphafetoprotein for patients with initial serum elevation of that marker. Patients who did not have an alphafetoprotein level obtained prior to initial therapeutic intervention will not be able to use AFP as a response criteria.

For high-risk patients being assessed at the end of Cycle 2, the assessment of response is based on central review of imaging, the alphafetoprotein values and sampling dates. The results of the central review will be returned to the institutional investigator within 3 weeks of submission of the imaging and AFP material. If there is a discrepancy between the assessment by central review and by institutional assessment, the study PI will discuss with the treating physician to resolve the discrepancy. If the investigator selects a post-induction regimen that is *not* indicated by the central review of response, the patient will be considered off protocol therapy as of the start date of consolidation therapy.

#### 10.3.1 Measurable Disease

The presence of at least one lesion that can be accurately measured in at least one dimension with the longest diameter at least 20 mm. With spiral CT scan, lesions must be at least 10 mm. The investigator will identify up to 10 MEASURABLE lesions to be followed for response.

Serial measurements of lesions are to be done with CT or MRI. The same method of assessment should be used to characterize each identified and reported lesion at baseline and during follow-up.

#### Quantification of Disease Burden

The sum of the longest diameter (LD) for all target lesions will be calculated and reported as the disease measurement.

#### Complete Response (CR)

Disappearance of all target lesions. Serum alphafetoprotein is normal for age for patients with initially elevated markers and for patients for whom markers were not obtained prior to initial therapy.

### Partial Response (PR)

#### **Either**

At least a 30% decrease in the disease measurement, taking as reference the disease measurement done to confirm measurable disease at study entry.

#### **OR**

Serum alphafetoprotein concentration decline of at least 90% of the highest AFP prior to the initiation of therapy ( $\geq 1 \log_{10}$ ) for patients with initially elevated markers in the absence of disease progression.

RECIST Measurement (% decline) =

$$\frac{\text{Sum of longest diameter of each measurable lesion at diagnosis} - \text{Sum of longest diameter of each measurable lesion after chemotherapy}}{\text{Sum of longest diameter of each measurable lesion at diagnosis}} \times 100\%$$

To be included in RECIST calculation liver lesions must be > 20 mm and pulmonary lesions must be > 10 mm at the time of diagnosis.

$$\% \text{ AFP decline} = \frac{(\text{Maximum AFP prior to beginning chemotherapy} - \text{Maximum AFP following chemotherapy})}{\text{Maximum AFP Prior to beginning chemotherapy}} \times 100\%$$

### For evaluation of window response

Maximum AFP prior to beginning chemotherapy should be used. If a biopsy is performed to make diagnosis, a repeat AFP should be obtained immediately prior to beginning chemotherapy (the same day). AFP following window chemotherapy should be drawn at the end of Cycle 2 (Week 6/7) just prior to beginning Cycle 3.

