Tumors that are unresectable at diagnosis, even if metastatic disease is present, should be referred to a surgical center with expertise in pediatric liver transplant and “extreme” liver resection should be done as soon as possible. Optimally for planning purposes, this liver transplant consultation should be obtained at diagnosis and no later than the FIRST DAY of the 3rd cycle of C5VD chemotherapy. The consent for the PLUTO registry should be obtained within one month of liver transplant and usually is obtained by the liver transplant team.

For the purposes of this study, consultation will be defined and may be accomplished in one of two ways:

- The FIRST TIME there is documented telephone or email/letter contact and a request for consultation between the treating oncologist and the liver specialty/transplant team.
- The FIRST TIME radiographic films and referral material are sent to the transplant physician/team at the same or another institution and are formally reviewed by the transplant physician/team.

The liver specialty/transplant physician/team will communicate the result of this consultation back to the referring physician.

Resection planning is to be completed before completion of the 4th cycle of C5VD chemotherapy. See Surgical Guidelines in [Section 13.0](#).

Patients will be evaluated after every 2 cycles of C5VD chemotherapy that occur prior to resection. Patients may have their primary tumor removed whenever it is feasible. It is the intent of the treatment that patients should have their tumors removed surgically or by OLT at the latest after Cycle 6 in both responders and

non-responders (ie, after the 4th cycle of C5VD) so that they can receive post-operative cycles of chemotherapy.

Chemotherapy should resume as soon as possible after surgical resection. In most circumstances this can typically be achieved within 3 weeks following surgery. **Patients who do not resume post resection chemotherapy within 42 days of resection will be considered off protocol therapy but not off study.** Further treatment will be at the discretion of the treating physician. Patients will continue to be followed on the AHEP0731 off protocol therapy follow-up CRF.

Regardless of the timing of surgery, patients should receive the total number of cycles as described above.

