**Patients whose tumors remain unresectable at the completion of planned therapy will be considered to have experienced an adverse EFS event. No further protocol therapy is planned for such patients. These patients can be treated at the discretion of the primary physician.**

Patients with pulmonary metastases will receive the first 2 cycles of Regimen H chemotherapy described above. If metastases disappear with chemotherapy, no pulmonary surgical intervention will be performed. If metastases are persistent after 4 total cycles of C5VD chemotherapy and the patient is considered a candidate for liver transplant at that time, metastases are to be resected to render the patient free of extrahepatic disease prior to transplant. Transplant may then be undertaken. If the liver tumor can be primarily resected after either 2 or 4 cycles of C5VD chemotherapy without transplant, this should be performed and the final cycles of chemotherapy should be administered. If the metastases are still present, they should then be resected. Pulmonary metastectomy may be performed earlier in the course of therapy if it can be done without resulting in delays in the administration of scheduled chemotherapy.

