- 3 Tumor evaluation, ultrasound, echocardiogram (or MUGA), and audiogram may be done within 28 days prior to enrollment. It is highly recommended that patients have echocardiogram (or MUGA) and audiogram prior to treatment, but if patient is emergently treated (see [Section 3.2.2](#)) these may be deferred until clinically stable, but must be done before beginning Cycle 2.
- 4 A liver transplant consult should be performed as soon as possible after diagnosis but no later than first day of 3rd C5VD Cycle. (i.e. no later than first day of Cycle 5.) (See [Section 13.1.5](#)).
- 5 Tumor disease evaluation performed after VIT Cycle 2 for all patients and after Cycles 4, 6 & 8 for non-responders and after Cycles 4, 6 and 10 for responders until tumor removed. No scans required once all tumor has been removed or resolved until the end of therapy (see [Section 15.3](#)).
- 6 Pathology slides required for patients following all surgical (biopsy/resection) procedures (see [Section 14.0](#)).
- 7 Tumor tissue is strongly encouraged to be submitted and can be submitted if consent has been obtained and patient is enrolled on ABTR01B1 or other appropriate study (See protocol for details.)
- 8 See [Section 15.0](#) for details. Ultrasound only needs repeating if initial U/S showed tumor thrombus & does not need to be performed once thrombus has resolved or surgery performed.

9 PRETEXT/POST-TEXT grouping should be done by radiologist, surgeon and oncologist on all scans performed at diagnosis and pre-operatively as appropriate. (See [Section 10.2](#) and [Appendix I](#)).

10 The same modality is to be used each time for consistency.

11 Consent for PLUTO registry should be obtained within one month of liver transplant, see [Section 13.4](#).

12 If a biopsy is performed to make diagnosis, a repeat AFP should be obtained immediately prior to beginning chemotherapy (the same day).

13 The AFP obtained at the end of Cycle 2/prior to Cycle 3 must be recorded on the Reporting Period 1 CRF and submitted for central review assessment of response. If an AFP was obtained post Cycle 2, do not repeat prior to Cycle 3. Note: The Reporting Period 1 CRF must be submitted without delay, see the Data Submission Schedule for details.

**This table only includes evaluations necessary to answer the primary and secondary aims. Obtain other studies as required for good patient care.**

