#### 13.1.5 Tumors Presenting with Metastatic Disease (Stage IV)

See [Section 14.0](#) for Pathology specimen requirements.

- Complete 2 cycles of upfront experimental window chemotherapy.
- Repeat radiographic imaging after completing upfront window therapy
  - Resect (non-extreme) tumors POST-TEXT 1 or 2 with > 1 cm radiographic margin on the middle hepatic vein, retrohepatic IVC, and portal bifurcation
  - For all others, proceed with 2 cycles of C5VD
- Repeat radiographic imaging after completing first 2 cycles of C5VD
  - Resect (non-extreme) tumors downstaged to POST-TEXT Group 1, 2, or 3 tumors with > 1 cm radiographic margin on right/left hepatic vein, retrohepatic IVC, and portal bifurcation.
  - For patients potentially needing liver transplant/extreme resection (see definition in [Section 13.1.3](#)), refer to surgical center with expertise in pediatric liver transplant and “extreme” liver resection at diagnosis if possible and no later than the FIRST DAY of the 3rd cycle of C5VD chemotherapy. Resection planning is to be completed before completion of Cycle 7 in high risk responders and before completion of Cycle 6 in high risk non-responders. Transplant or “extreme” resection is to occur within 4 weeks of completing the 7th cycle of chemotherapy in high risk responders and the 6th cycle of chemotherapy in high-risk non-responders.
  - Repeat chest CT scan must demonstrate complete clearance of pulmonary metastatic disease within 1 week prior to liver transplant.
  - Those patients with persistent extrahepatic disease, may be resected (not transplanted) at the discretion of the surgical center with expertise in pediatric liver transplant and “extreme” liver resection.
  - Those patients with persistent extrahepatic disease who are not anatomically resectable without transplantation will continue chemotherapy.

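### In Stratum 4, the AFP that can by itself establish a partial response to VIT may be drawn after a resection directed between Cycles 2 and 3

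*Combined protocol and SAP*

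**What the plan says.** Hypothesis 1.3 in Section 9.2 judges Stratum 4 on disease status after the two VIT window cycles. Under Sections 10.3.1 and 10.3.3, an AFP fall of at least 90% from the highest pre-treatment value is enough for a partial response if the marker was elevated at the start and no lesion has progressed.

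Section 10.3.1 times the deciding sample: "AFP following window chemotherapy should be drawn at the end of Cycle 2 (Week 6/7) just prior to beginning Cycle 3". Footnote 13 of the Section 7.5 table reads "The AFP obtained at the end of Cycle 2/prior to Cycle 3 must be recorded on the Reporting Period 1 CRF" and adds "If an AFP was obtained post Cycle 2, do not repeat prior to Cycle 3".

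Section 13.1.5, on Stage IV disease, has sites complete the two window cycles and then gives two steps. The first is "Repeat radiographic imaging after completing upfront window therapy". The second is "Resect (non-extreme) tumors POST-TEXT 1 or 2 with > 1 cm radiographic margin on the middle hepatic vein, retrohepatic IVC, and portal bifurcation". Everyone else goes on to two cycles of C5VD, so this resection falls between Cycle 2 and Cycle 3. Section 4.6 adds "Patients may have their primary tumor removed whenever it is feasible" and allows up to 42 days after resection before chemotherapy must resume.

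**The concern.** Removing the primary removes a major source of AFP. If the only post-window AFP is drawn after that operation, the measured fall mixes the effect of VIT with the effect of surgery. A patient with stable disease on the post-window scan could then meet the 90% criterion and be counted as a VIT responder.

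Two things depend on this classification. One is the two-stage test of the response rate against 45%. The other is the patient's further treatment, because Section 4.6 gives responders two more VIT cycles.

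The plan deals with this kind of contamination at baseline only. Section 10.3 bars AFP as a criterion when no level was obtained before the initial intervention, and Section 10.3.1 asks for a repeat level after a diagnostic biopsy. The post-window side has no matching rule.

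**Working it through.** **Order of events**

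1. Cycle 2 occupies Weeks 4-6 and Cycle 3 is mapped to start in Week 7 (maps 4.6.9, 4.6.10.a and 4.6.11.a).
2. The post-window scan comes next, and qualifying tumors are then resected (Section 13.1.5).
3. Cycle 3 follows. After a resection it typically starts within 3 weeks and at most 42 days later (Section 4.6).
4. The response AFP may be the end-of-Cycle 2 value or the pre-Cycle 3 value (Section 7.5, footnote 13). In a resected patient these lie on opposite sides of the operation.
5. The Day 21 row of map 4.6.9 lists codes f, g and h. AFP belongs to code c, which is not in that row. The Section 7.5 table does mark AFP under End of Cycle 2, so the sample is scheduled there although the map row omits it.

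**The plan's own figures**

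Inputs from Section 9.2: 22 evaluable patients at the first stage, continue with 10 or more responders; 19 more at the second, success with 23 or more of 41.

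- P(stop early) = P(X1 ≤ 9), with X1 ~ Bin(22, p).
- P(accept) = Σ over x = 10 to 22 of P(X1 = x) × P(X2 ≥ 23 − x), with X2 ~ Bin(19, p).

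At p = 0.45, P(stop early) = 0.435 and P(accept) = 0.100, so rejection is 0.900. At p = 0.65, P(accept) = 0.907. The plan states 0.435, 0.90 and 0.90, so its figures are reproduced.

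**Sensitivity to misclassification**

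The documents do not say how many patients would be affected. Suppose that, on average, k of 41 true non-responders are scored as responders. The apparent rate is then 0.45 + k/41.

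| k per 41 (assumed) | Apparent rate | P(stop early) | P(accept) |
|---|---|---|---|
| 0 | 0.450 | 0.435 | 0.100 |
| 1 | 0.474 | 0.346 | 0.167 |
| 2 | 0.499 | 0.266 | 0.257 |
| 3 | 0.523 | 0.196 | 0.367 |

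Expected non-responders at 45% are 41 × 0.55 = 22.55. The range k = 1 to 3 therefore means converting 1/22.55 = 4.4% to 3/22.55 = 13.3% of them.

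**The case against.** The strongest reply is that several provisions already point to a pre-surgical value:

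- Section 7.5 marks an AFP under End of Cycle 2.
- The timing sentence names Week 6/7, and Section 7.0 tolerates departures of only 72 hours for disease evaluations. A sample taken weeks after surgery would usually be off schedule.
- An AFP drawn after Cycle 2 is not to be repeated before Cycle 3.
- The AFP formula takes the highest value after chemotherapy, so a pre-surgical value would outrank a lower later one.
- Central review receives AFP sampling dates.

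The exposed group is also narrow. It needs stable disease on the scan, a POST-TEXT 1 or 2 tumor with a clear margin, resection straight after the window, no earlier post-window AFP, and a 90% fall by the later draw. Section 2.5 further speaks of an optimal six-week period without temsirolimus before definitive resection, which may discourage surgery at that point.

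All of this stands as a limit on frequency, but it does not close the gap. The do-not-repeat note and the highest-value rule help only if a pre-surgical sample exists. Footnote 13 accepts the pre-Cycle 3 value, and the Week 6/7 wording conflicts with the pre-Cycle 3 wording once surgery delays Cycle 3. No text tells central review what to do with a post-resection date.

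A reader might also infer that the lesion sum can be taken after surgery, since its formula refers only to "Sum of longest diameter of each measurable lesion after chemotherapy" and Section 4.6 says "Pulmonary metastectomy may be performed earlier in the course of therapy if it can be done without resulting in delays". The documents do not support that reading. Section 13.1.5 puts the scan before the resection and uses it to select who is operated on. Section 15.3 requires those images to be submitted as soon as acquired, and Section 9.2 fixes the endpoint after two cycles. Sections 4.6 and 13.3 both put the window chemotherapy first for patients with lung metastases.

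**Conclusion.** The point holds for AFP only. As written, the plan admits a post-resection AFP as the deciding value when no earlier post-window sample exists, and that value alone can produce a partial response in the Stratum 4 primary endpoint.

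The number of patients affected is unknown and probably small. The rise from 0.100 to about 0.17, 0.26 or 0.37 rests on an assumed 1 to 3 patients per 41. It shows how sensitive the two-stage rule is to misclassification and is not an estimate of the trial's actual error rate. Nor do the documents establish that a resected non-responder would necessarily reach a 90% fall, because they give no post-resection AFP course and Stage IV patients may still have metastases.

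Separately, Section 2.5 (the temsirolimus-free period) and Section 13.1.5 (resection after the window) must be reconciled, since together they leave the timing of this surgery unclear.

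**What to change.** State in Section 10.3, in Section 7.5 footnote 13 and in the Day 21 row of map 4.6.9 that the response AFP is the one drawn at the end of Cycle 2 and before any resection of primary or metastases. Add that an AFP drawn after resection cannot establish response, so a patient without a pre-resection value is classified on the post-Cycle 2 imaging alone. No new rule for lesion measurements is needed.

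The cost is two sentences and one code on the map. The sample is already scheduled, and no operation or dose changes. The front matter gives a closing date of July 20, 2018, so for data already collected the rule can be applied from the recorded AFP and surgery dates, with the number of reclassified patients reported.

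The small downside is that a true AFP-only responder who lacks a pre-resection sample would count as a non-responder.

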### Progressive Disease (PD)

At least a 20% increase in the disease measurement, taking as reference the smallest disease measurement recorded since the start of treatment, or the appearance of one or more new lesions.

### Stable Disease (SD)

Neither sufficient shrinkage to qualify for PR nor sufficient increase to qualify for PD taking as reference the smallest disease measurement since the treatment started. Serum alpha fetoprotein concentration does not increase for patients with initially elevated markers.

### Response Assessment

Each patient will be classified according to their “best response” for the purposes of analysis of treatment effect. Best response is determined from the sequence of the objective statuses described above.

#### 10.3.2 Non-measurable Metastatic Disease

Non-target lesions: Includes all lesions that do not qualify as measurable disease at diagnosis. These lesions should be noted and recorded and response indicated as improved, no change or worse. These lesions should not be included as part of RECIST calculations.

### 10.3.3 Overall response assessment

The overall response assessment takes into account response in the measurable and non-measurable disease, and the appearance of new lesions, where applicable, and decline of alphafetoprotein according to the criteria described in the table below.

Target Lesions	Non-target Lesions	New Lesions	Tumor Markers	Overall Response
CR	CR	No	Normalized 	CR 
CR	Incomplete response/SD	No	Decreased	PR
PR	Non-PD	No	Decreased	PR
NON-PD	Non-PD	No	≥ 90% decrease from highest AFP prior to treatment (1 log 10 decreased)	PR
SD	Non-PD	No	Stable	SD
PD	Any	Yes or No	Any	PD
Any	PD	Yes or No	Any	PD
Any	Any	Yes	Any	PD

 An overall response of CR MUST include a normal AFP. Until the AFP has normalized, a patient can be considered PR at best.

It is not uncommon for a patient to complete therapy and have an AFP that remains minimally elevated. If there is no evidence of persistent clinical or radiographic disease, these patients can be followed as in [Section 7.6](#)

A rise in AFP by itself will not be considered as progressive disease. If an AFP level is elevated compared to a previous level then weekly AFP measurements should be considered. Radiographic studies (CT chest and CT or MRI abdomen) should be considered in patients with an elevated AFP in an attempt to try and identify progressive disease.

